1.3.2 Study flow chart - Triplet cohort

Procedure	Pre-screening ^a	Screening ^b	Treatment cycle 1		Treatment cycle 2 +		End of treatment	90 (± 7) Days (3 month) Follow-up ^d	Notes*
Day		Days to first infusion	D1		21 (± 3) days from previous infusion		30 (± 5) days from last infusion		
			Pre-infusion ^c	EOI	Pre-infusion ^c	Every 6 weeks (± 7 days)			
CEACAM5 expression status ^a (archival or fresh tumor tissue) – central IHC/ prescreening Informed consent	X								
Informed Consent		X							
Inclusion/exclusion criteria		≤ 28	X						Section 5.1, 5.2
Demography, medical/surgical/disease/smoking history ^e		≤ 28							
NSCLC characteristics ^f	X	≤ 28							
Height		≤ 7							
Performance status (ECOG)		≤ 7	X		X		X	X	Section 8.2.1, 8.2.3
Physical examination, including vital signs, body weight ^g		≤ 7	X		X		X	X	Section 8.2.1
Hematology ^h		≤ 7	X		X		X		Section 8.2.5, 10.2 (Appendix 2)
Coagulation ⁱ		≤ 7	X		X		X		Section 10.2 , (Appendix 2)
Clinical blood chemistry ^j		≤ 7	X		X		X		Section 8.2.5, 10.2 (Appendix 2)
Thyroid function		≤ 7			X		X		
Urinalysis ^k		≤ 7	X		X				Section 10.2 , (Appendix 2)
HBsAg & HCV serology and HIV test (only if required at country level)		X							Section 10.8 , (Appendix 8)

Procedure	Pre-screening ^a	Screening ^b	Treatment cycle 1		Treatment cycle 2 +		End of treatment	90 (± 7) Days (3 month) Follow-up ^d	Notes*
Day		Days to first infusion	D1		21 (± 3) days from previous infusion		30 (± 5) days from last infusion		
			Pre-infusion ^c	EOI	Pre-infusion ^c	Every 6 weeks (± 7 days)			
Urine or Serum pregnancy test ^l		≤ 7			X		X	X	Section 10.2 (Appendix 2) Section 10.5 (Appendix 5)
Left ventricular ejection fraction (MUGA/echocardiogram) ^m		≤ 28							Section 8.2.4.2
12-lead ECG ⁿ		≤ 7	X	X	X		X		Section 8.2.4.1
Specific ocular tests ^o		≤ 28					X		Section 8.2.2
Tusamitamab ravtansine/Ramucirumab/Pembrolizumab administration			X		X				Section 6.1
AE assessment ^p	X		Continuously throughout the study period						Section 8.2, 8.3, 10.3 (Appendix 3)
Concomitant medication ^q		X	Continuously throughout the study period						Section 6.5
Tumor assessment – RECIST v1.1 - CT/MRI; relevant surrogate markers ^r		≤ 28				X	X	X	Section 8.1
Circulating CEA ^s	X	≤ 28				X	X	X	
IgG			X						
Record further anticancer therapy								X	
Tusamitamab ravtansine PK			Refer to PK/ATA flowchart, Section 1.3.3						Section 8.5
Tusamitamab ravtansine Immunogenicity			Refer to PK/ATA flowchart, Section 1.3.3						Section 8.9

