- j Clinical blood chemistry: Liver function tests: SGOT (AST), SGPT (ALT), total bilirubin, conjugated bilirubin, AP. Renal function tests: Urea (or BUN) & creatinine. Electrolytes: Sodium, potassium, calcium, glucose. Others: LDH, albumin and total proteins. During first cycle, liver function tests will be performed weekly. The liver function tests and renal function tests will be done before IMP administration at each cycle, unless clinically appropriate. In case of Grade ≥ 3 liver function abnormal tests, additional tests will be repeated every 2-3 days until recovery to baseline value.
- k Urinalysis tests on morning spot will be performed by dipstick at baseline, and at every treatment cycle. In case of proteinuria $\geq ++$ (dipstick), proteinuria quantification by proteinuria/24 h should be performed.
- l Serum pregnancy test: women of childbearing potential must have a negative serum pregnancy test result within 7 days prior to the initial dose of IMP. A pregnancy test (serum/urine) will be repeated every 4 weeks before IMP administration, and a serum test will be repeated at the End of Treatment evaluation (30 \pm 5 days after the last IMP administration), and at the Follow-up visit (90 \pm 7 days after last IMP dose).
- m Echocardiogram or MUGA scan: left ventricular ejection fraction (LVEF) will be evaluated during screening period, and whenever clinically indicated.
- n 12-lead ECG is required at baseline (In case the ECG performed less than 7 days before 1st IMP administration is considered as normal, there is no need to repeat it just before the 1st IMP) before starting and after completing the first IMP administration (within 30 minutes after the end of tusamitamab ravtansine infusion); before IMP administration at each cycle; and at the End of treatment evaluation, 22 to 30 days after last IMP administration.
- o Specific ocular tests will include assessment of ocular/visual symptoms and ocular exams including visual acuity, slit lamp under dilatation, and Schirmer's test at screening and whenever clinically indicated.
- p AE: For participant who was prescreened and had fresh biopsy, only the Adverse Events related to the fresh biopsy procedure itself should also be reported in eCRF as general requirement of AE/SAE with the reporting time frame interval of 1 month for the prescreening period after fresh biopsy.

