2.3 BENEFIT/RISK ASSESSMENT

To date, efficacy and safety data from ongoing studies of tusamitamab ravtansine (TED13751, TCD15054, ACT16146, ACT16444, ACT16525, ACT16432 and EFC15858) support continued clinical development of tusamitamab ravtansine. Information about the known and expected benefits, risks, and reasonably anticipated AEs with tusamitamab ravtansine may be found in the Investigator's Brochure (IB). Based on available safety data, the main anticipated risk to patients is corneal toxicity presenting as microcystic keratopathy/keratitis, which is reversible and manageable with dose delay and dose reduction in some patients. Peripheral neuropathy is an identified risk.

Other potential risks include colitis (including hemorrhagic), cardiotoxicity (myocardial or conduction abnormalities), hematologic cytopenia, and hepatotoxicity, as well as systemic acute hypersensitivity (including anaphylaxis) and, in patients who received tusamitamab ravidansine in peripheral veins, local infusion site reactions to tusamitamab ravidansine (6).

Ramucirumab, a human IgG1 monoclonal antibody that inhibits VEGFR-2, is approved in combination with docetaxel for the treatment of patients with metastatic NSCLC. Given the considerable risks of adverse effects including neutropenia, anemia, and infection associated with docetaxel, the combination of tusamitamab ravidansine with ramucirumab may represent a treatment regimen with an improved safety profile as compared to the approved combination of docetaxel and ramucirumab. More detailed information about the known and expected benefits and risks and reasonably expected adverse effects of ramucirumab may be found in the US Package Insert or Summary of Product Characteristics for Cyramza®.

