5.2 EXCLUSION CRITERIA

Participants are excluded from the study if any of the following criteria applies:

Medical conditions

E 01. Untreated brain metastases and history of leptomeningeal disease. Patients with previously treated brain metastases may participate provided they are stable (ie, without evidence of progression by imaging for at least 4 weeks prior to the first administration of study intervention, and any neurologic symptoms have returned to baseline); there is no evidence of new or enlarging brain metastases; and the patient does not require any systemic corticosteroids to manage brain metastases within 3 weeks prior to the first dose of study intervention.

E 02. Significant concomitant illness, including any severe medical condition that, in the opinion of the investigator or Sponsor, would impair the patient's participation in the study or interpretation of the results.

- E 03. History within the last 3 years of an invasive malignancy other than that treated in this study, with the exception of resected/ablated basal or squamous-cell carcinoma of the skin or carcinoma in situ of the cervix, or other local tumors considered cured by local treatment.
- E 04. History of known acquired immunodeficiency syndrome (AIDS)-related illnesses or known human immunodeficiency virus (HIV) disease requiring antiretroviral treatment; or active infection with hepatitis A, B (defined as either positive HBs antigen or positive hepatitis B viral DNA test above the lower limit of detection of the assay), or C (defined as known positive result for antibodies to hepatitis C and known quantitative hepatitis C virus [HCV] RNA results greater than the lower limit of detection of the assay).
- E 05. Non-resolution of any prior treatment-related toxicity to < Grade 2 according to NCI CTCAE V5.0, with the exception of alopecia, vitiligo, or active thyroiditis controlled with hormone replacement therapy.
- E 06. Unresolved corneal disorder or any previous corneal disorder considered by an ophthalmologist to predict higher risk of drug-induced keratopathy. The use of contact lenses is not permitted. Patients using contact lenses who are not willing to stop wearing them for the duration of the study intervention are excluded.
- E 07. Radiographic evidence of major airway or blood vessel invasion or intratumor cavitation, regardless of tumor histology.
- E 08. History of uncontrolled hereditary or acquired arterial thrombotic disorder or history of aneurism.

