- E 25. Washout period before the first administration of study intervention of less than 3 weeks or less than 5 times the half-life, whichever is shorter, for prior antitumor therapy (chemotherapy, targeted agents, immunotherapy and radiotherapy, or any investigational treatment).
- E 26. Contraindication to use of corticosteroid premedication.
- E 27. Current therapeutic anticoagulation with warfarin, low-molecular-weight heparin, or similar agents. Patients receiving prophylactic, low-dose anticoagulation therapy are eligible provided that the coagulation parameters defined in the inclusion criteria (INR \leq 1.5 or PT \leq 1.5 \times ULN, and PTT/aPTT \leq 1.5 \times ULN) are met.

Prior/concurrent clinical study experience

- E 28. Previous enrollment in this study, current participation in any other clinical study involving an investigational study treatment, or any other type of medical research.

Diagnostic assessments

E 29. Poor organ function as defined by any one of the following prior to IMP administration:

- a) Serum creatinine $>1.5 \times$ upper limit of normal (ULN) or 1.0 to $1.5 \times$ ULN with estimated glomerular filtration rate (eGFR) $<60 \text{ mL/min}/1.73 \text{ m}^2$ as estimated using a Modification of Diet in Renal Disease (MDRD) formula.
- b) Total bilirubin $>1.0 \times$ ULN.
 - aspartate aminotransferase (AST), alanine aminotransferase (ALT) $>2.5 \times$ ULN or
 - AST, ALT $>5 \times$ ULN in case of documented liver metastasis
 - or
 - AST, ALT $>1.5 \times$ ULN concomitant with alkaline phosphatase (ALP) $>2.5 \times$ ULN. ALP $>5 \times$ ULN with normal ALT/AST, for patients with bone metastases.
- c) Neutrophils $<1.5 \times 10^9/\text{L}$
 - or
 - platelet count $<100 \times 10^9/\text{L}$
 - or
 - hemoglobin $<9 \text{ g/dL}$ (blood infusion-free for at least 2 weeks).

E 30. Urine dipstick or routine analysis indicating proteinuria of 2+ or higher, unless a 24 hour urine collection demonstrates $<1000 \text{ mg}$ of protein.

Other exclusions

- E 31. Individuals accommodated in an institution because of regulatory or legal order; prisoners or subjects who are legally institutionalized.
- E 32. Any country-related specific regulation that would prevent the subject from entering the study - see Appendix 8: Country-specific requirements ([Section 10.8](#)).

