8.2.6.5 Liver function tests

Hepatic enzyme increase has been reported with tusamitamab ravtansine administration as monotherapy or ramucirumab. Patients should be carefully followed and in case of Grade ≥ 3 abnormal liver function tests, additional liver function tests will be done every 2 to 3 days until recovery to baseline value. Tusamitamab ravtansine should be permanently discontinued in case of drug-induced Grade 4 liver enzyme increase. For stopping rules for ramucirumab administration, the current product leaflet should be followed.

Grade ≥ 3 (ie, $> 5 \times$ ULN) increased liver enzyme events should be reported as AESIs.

8.2.6.6 *Hypertension*

An increased incidence of severe hypertension (CTCAE Grade 3) has been reported in patients receiving ramucirumab as compared with placebo. In most cases, hypertension was controlled using standard antihypertensive treatment. Preexisting hypertension should be controlled before starting ramucirumab treatment. Monitoring of blood pressure is required during ramucirumab therapy. Every attempt should be made to control blood pressure to systolic <140 mmHg and diastolic <90 mmHg prior to starting treatment with ramucirumab. Routine clinical and laboratory monitoring is required in patients who again develop hypertension or experience a deterioration in previous hypertension.

Withhold ramucirumab for severe hypertension until medically controlled. Permanently discontinue ramucirumab for medically significant hypertension that cannot be controlled with antihypertensive therapy or in patients with hypertensive crisis or hypertensive encephalopathy.

8.2.6.7 *Proteinuria*

Proteinuria is an adverse effect for all therapies targeting the vascular endothelial growth factor (VEGF)/VEGFR-2 pathway, including ramucirumab. Proteinuria has been associated with ramucirumab in clinical studies; the majority of events were Grade 1 or 2.

Monitor proteinuria by urine dipstick and/or urinary protein creatinine ratio. If the result of the urine dipstick is 2+ or greater, perform a 24 hours urine collection for protein measurement.

Withhold ramucirumab for urine protein levels of 2 or more grams collected over 24 hours. Reinitiate ramucirumab at a reduced dose once the urine protein level returns to less than 2 grams over 24 hours. Permanently discontinue ramucirumab for urine protein levels greater than 3 grams over 24 hours, or in the setting of nephrotic syndrome.

8.2.6.8 *Bleeding/Hemorrhage*

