Immune-mediated hepatitis	AST or ALT greater than 3 but no more than 5 times the ULN or total bilirubin greater than 1.5 but no more than 3 times the ULN	Withhold
Immune-mediated endocrinopathies	Grades 3 or 4	Withhold until clinically stable
Immune-mediated nephritis	Grade 2	Withhold
	Grades 3 or 4	Permanently discontinue
Immune-mediated skin adverse reactions	Grade 3 or suspected Stevens-Johnson Syndrome (SJS) or toxic epidermal necrolysis (TEN)	Withhold
	Grade 4 or confirmed SJS or TEN	Permanently discontinue
Other immune-mediated adverse reactions	Grades 2 or 3 based on the severity and type of reaction	Withhold
	Grade 3 based on the severity and type of reaction or Grade 4	Permanently discontinue
Recurrent immune-mediated adverse reactions	Recurrent Grade 2 pneumonitis	Permanently discontinue
	Recurrent Grades 3 or 4	
Inability to taper corticosteroid	Requirement for 10 mg per day or greater prednisone or equivalent for more than 12 weeks after last dose of pembrolizumab	Permanently discontinue
Persistent Grade 2 or 3 adverse reaction (excluding endocrinopathy)	Grades 2 or 3 adverse reactions lasting 12 weeks or longer after last pembrolizumab	Permanently discontinue

General instructions:

1. Corticosteroid taper should be initiated upon AE improving to Grade 1 or less and continue to taper over at least 4 weeks.
2. For situations where pembrolizumab has been withheld, pembrolizumab can be resumed after AE has been reduced to Grade 1 or 0 and corticosteroid has been tapered.
3. For severe and life-threatening irAEs, IV corticosteroid should be initiated first followed by oral steroid. Other immunosuppressive treatment should be initiated if irAEs cannot be controlled by corticosteroids.

For additional guidelines, please refer to ASCO Guidelines published in 2021 ([24](#)).

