10.8 APPENDIX 8: COUNTRY-SPECIFIC REQUIREMENTS

Serology for HBsAg and HCV and HIV test at screening will be performed only if required at the country level.

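### Exclusion E04 defines active hepatitis B by a test result, but the triplet cohort is tested for HBsAg only where a country requires it

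*Protocol*

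**What the plan says.** E04 in protocol Section 5.2 treats its infections differently. The HIV limb covers known AIDS-related illness or known HIV disease under antiretroviral treatment. The hepatitis C limb needs a known antibody result and a known RNA result. The hepatitis B limb excludes "active infection with hepatitis A, B (defined as either positive HBs antigen or positive hepatitis B viral DNA test" above the assay's detection limit, and the word *known* does not appear in it.

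On testing, Appendix 8 (Section 10.8) says: "Serology for HBsAg and HCV and HIV test at screening will be performed only if required at the country level". The triplet flow chart (Section 1.3.2) has a screening row, "HBsAg & HCV serology and HIV test (only if required at country level"), which points to Section 10.8. Table 18 in Appendix 2, the list of required laboratory tests, contains no hepatitis serology. The triplet-only exclusions E38 to E46 add none, and HBV DNA is not scheduled anywhere.

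Section 4.1 says all eligibility criteria are checked during screening. Section 8 requires screening evaluations to be completed and reviewed to confirm them. Section 5 permits no waivers.

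**The concern.** An exclusion defined by a laboratory result works only if the result exists. Where the country does not require the test and the participant has no earlier HBsAg or HBV DNA result, a site can follow the protocol exactly and still dose someone whom E04 excludes. Known carriers are still kept out; the gap concerns undiagnosed ones.

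What is at stake is liver safety under three drugs:

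- Section 2.3 says of tusamitamab ravtansine: "Other potential risks include colitis (including hemorrhagic), cardiotoxicity (myocardial or conduction abnormalities), hematologic cytopenia, and hepatotoxicity".
- Section 8.2.6.5 says: "Hepatic enzyme increase has been reported with tusamitamab ravtansine administration as monotherapy or ramucirumab".
- Appendix 4 has pembrolizumab withheld for immune-mediated hepatitis at "AST or ALT greater than 3 but no more than 5 times the ULN", or at a raised bilirubin.

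Management also depends on cause. Section 8.2.6.5 stops tusamitamab ravtansine permanently for a drug-induced Grade 4 enzyme rise, while Appendix 4 directs corticosteroids for severe immune-related events. With no baseline HBsAg result, attributing a liver event takes longer.

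**Working it through.** **Step 1: does the testing condition cover HBsAg?** The parenthesis in the flow chart row could be read as applying to the HIV test alone. Appendix 8, which the row cites, applies it to all three tests. HBsAg is therefore conditional.

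**Step 2: can *known* be read into the hepatitis B limb?** No. In E04 the HIV wording ends at a semicolon before the hepatitis limbs begin. The hepatitis C limb then uses *known* twice, which would be redundant if an earlier *known* carried through. Only the B limb is defined by a result without that qualifier.

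**Step 3: does another required test close the gap?** Other test-defined exclusions are paired with an unconditional screening test: LVEF (E11), organ function (E29), proteinuria (E30) and, in the triplet, TSH (E46). Hepatitis B is not.

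The nearest substitute is E29, "Poor organ function as defined by any one of the following prior to IMP administration". Its liver limits exclude:

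- total bilirubin above 1.0 × ULN;
- AST/ALT above 2.5 × ULN, or above 5 × ULN with liver metastases;
- AST/ALT above 1.5 × ULN together with ALP above 2.5 × ULN.

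These measure liver function, not infection. A carrier with normal bilirubin and, for example, AST/ALT at 2 × ULN with normal ALP is not excluded by them.

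**Step 4: how many participants?** The documents give no HBsAg prevalence, no list of countries that require testing, and no share of participants with an existing result. Only bounds follow:

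- Lower bound: 0 unchecked, if every country tests or every participant already has a result.
- Upper bound: all 6 to 12 DLT-evaluable participants (Section 9.2.3), if neither holds, plus any non-evaluable participants who were dosed and replaced.

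**Step 5: how many assays would universal testing need?** Inputs from Section 9.2: 74 prescreened, 79% prescreening failure, 23% screen failure, up to 12 DLT-evaluable.

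- The plan's own figure: 12 / (0.21 × 0.77) = 12 / 0.1617 = 74.2, so 74 is reproduced.
- Screened: 74 × (1 − 0.79) = 15.54. Passing screening: 15.54 × (1 − 0.23) = 11.97.
- Screened to obtain 6: 6 / 0.77 = 7.79. Screened to obtain 12: 12 / 0.77 = 15.58.
- Each replacement of a DLT-non-evaluable participant (Section 4.1): 1 / 0.77 = 1.30 further screened.

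This gives about 8 to 16 HBsAg assays, plus about 1.3 per replacement, and fewer where countries already test.

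**The case against.** The strongest reply is that country-conditional testing is a deliberate choice, stated consistently in both flow charts and Appendix 8. E04 excludes active infection, and a definition does not by itself order a test. Hepatitis A in E04 and active tuberculosis in E40 also have no scheduled test. If one missing word is the problem, adding *known* to the hepatitis B limb would cure it. Insisting on a test for B while leaving hepatitis C conditional looks selective, since an undiagnosed hepatitis C carrier faces the same liver risks. The documents also do not say that any study drug provokes a hepatitis B flare, and every participant has already received an anti-PD1/PD-L1 agent (I03).

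There are safeguards too. The flow chart states: "During first cycle, liver function tests will be performed weekly"; Section 8.2.5 extends this to the first two cycles. Section 6.6.3 sets bilirubin and transaminase limits for each retreatment. Grade 3 or higher enzyme rises are adverse events of special interest, and the Study Committee meets regularly. Section 10.3.3 obliges a causality work-up, to which hepatitis B tests can be added. Appendix 2 lets investigators order extra tests.

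Part of this stands. The frequency is unknown, no flare mechanism is documented, and monitoring limits the consequence of a missed carrier, so attribution is delayed rather than lost. The rest does not remove the mismatch. The monitoring acts after dosing, whereas an exclusion should act before it, and discretionary testing is optional. Hepatitis A and tuberculosis are not defined by a test result in the protocol. Adding *known* would align the wording but would weaken the exclusion as now written and still admit an undiagnosed carrier. Treating C differently follows E04's own terms, which restrict that limb to known results.

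**Conclusion.** The concern holds. The protocol sets a result-based exclusion for hepatitis B and does not ensure that the result is obtained for triplet participants in countries without a testing rule. Its size, in participants unchecked or in carriers dosed, cannot be stated beyond the bounds above. No effect on the RP2D decision is claimed.

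The doublet flow chart has the same row, but the SAP version history places SAP v2.0 after the last participant's last visit, so doublet screening appears finished. SAP Section 1.1 says the triplet had not started. The point is therefore limited to the triplet. It is worth correcting because the gap between criterion and procedure is clear and the remedy is small; it does not undermine the trial's analysis.

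**What to change.** In Appendix 8 and in the HBsAg row of the triplet flow chart, require an HBsAg result for every triplet participant before first dose, taken from the blood already drawn at screening. Add HBV DNA if HBsAg is positive or in doubt. Give the row a time window, since it now shows only a mark; a routine-care result obtained before consent could then count under Section 8. HCV and HIV tests can remain country-conditional.

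The cost is the 8 to 16 assays worked out above, with a possible extra screen failure. It also needs a short protocol amendment, with IRB/IEC approval before implementation (Section 10.1.1).
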